2. ABBREVIATIONS AND ACRONYMS

Abbreviation or Specialist Term	Explanation
AE	Adverse event
ADI	Actual Dose Intensity
ALT	Alaine Aminotransferase
ANC	Absolute neutrophile count
AST	Aspartate Aminotransferase
ATC	Anatomical Therapeutic Class
AUC	Area under
BID	Twice-daily
BOIN	Bayesian optimal interval
BOR	Best overall response
CA-125	Cancer antigen 125
CBR	Clinical benefit rate

Abbreviation or Specialist Term	Explanation
CI	Confidence Interval
CR	Complete response
CSR	Clinical Study Report
CTCAE	Common Terminology Criteria for Adverse Event
СҮР	Cytochrome P450
C _{max}	Maximum observed plasma concentration
C _{min}	Minimum observed plasma concentration
ctDNA	Circulating tumor DNA
DOR	Duration of response
DLT	Dose-limiting toxicity
ECG	Electrocardiogram
ECOG	Eastern Cooperative Oncology Group
EOT	End-of-treatment
eCRF	Electronic case report form
FISH	DNA fluorescent in situ hybridization
GCIG	Gynecologic Cancer Intergroup criteria
ICF	Informed consent Form
IHC	Immunohistochemistry
INRC	International Neuroblastoma Response Criteria
LLOQ	Lower limit of quantitation
MTD	Maximum Tolerated Dose
MR	Minor Response
MedDRA	Medical Dictionary for Regulatory Activities
NCA	Non-compartmental analysis
NCCN	National Comprehensive Cancer Network
NCI	National Cancer Institute
NE	Not evaluable
NGS	Next generation sequencing
OHC	4β-hydroxycholesterol
ORR	Objective response rate

Abbreviation or Specialist Term	Explanation
PCWG3	Prostate Cancer Working Group criteria
PD	Progressive disease
PDI	Planned Dose Intensity
PFS	Progression-free survival
PLK4	Polo-Like Kinases 4
PK	Pharmacokinetic
PR	Partial response
PSA	Prostate specific antigen
PT	Preferred Term
QD	Daily
RBC	Red blood cell
RECIST	Response Evaluation Criteria in Solid Tumors
SAE	Serious Adverse Event
SAP	Statistical Analysis Plan
SD	Stable disease
SOC	System organ classification
SRC	Safety Review Committee
TEAE	Treatment-emergent adverse events
TL	Target lesion
T_{max}	Time to maximum observed plasma concentration
t _{1/2}	Elimination half-life
ULN	Upper limit of normal
VAF	Variant allele frequency
WHODrug	World Health Organization Drug

3. INTRODUCTION

This document describes the statistical methods to be implemented in the statistical analysis of data collected under clinical study Protocol RP-1664-01, titled: "Phase 1 Trial of the Safety, Pharmacokinetics (PK), Pharmacodynamics, and Preliminary Clinical Activity of RP-1664 in Participants with Advanced Solid Tumors". This Statistical Analysis Plan (SAP) contains definitions of analysis populations, derived variables, statistical methods for the analyses of baseline, efficacy, and safety data and the data listings and summary tables which will be produced. Details will be described to ensure the results are complete and appropriate to allow valid conclusion regarding the study objectives.

The analysis details for pharmacokinetic, pharmacodynamics, and biomarker analyses are not described within this SAP. A separate analysis plan may be implemented for those analyses.

This document has been prepared based on Protocol Version 3.0, dated March 24, 2025.

4. STUDY OVERVIEW

This is a multicenter, open-label Phase 1 trial to investigate the safety, PK, pharmacodynamic, and preliminary efficacy of the PLK4 inhibitor RP-1664 in participants with molecularly selected advanced solid tumors. The trial is estimated to enroll approximately 80 evaluable participants with solid tumors harboring any one of the following:

4.1 Study Design

The trial will follow a Bayesian Optimal Interval (BOIN) design to guide escalation and de-escalation decision, establish a maximum tolerated dose (MTD), and identify a dose and schedule of RP-1664 that is tolerable.

All participants will undergo a PK evaluation period starting at Cycle 0 Day 1. Participants will be assigned to receive either a single dose of RP-1664 at the highest Safety Review Committee (SRC) approved dose level with PK collection over the subsequent 48 hours to characterize the half life (t1/2) of RP-1664 in the fasted state or enrolled into a cohort to investigate the effect of food on RP-1664 PK.

The starting dose (Dose Level 1) is 10 mg once daily (QD). RP-1664 will initially be given QD on a 2 weeks on 1 week off schedule to allow 1 week for bone marrow recovery.

The first escalation (Dose Level 2) will be up to 30 mg to limit the number of participants receiving a potentially subtherapeutic dose. After Dose Level 2, escalation will proceed with up to 100% increases in RP-1664 after evaluation of tolerability by the SRC until Dose Level S. Dose Level S is defined as the dose level at which any of the following safety signals occur during Cycle 0 or Cycle 1:

- Any \geq Grade 3 hematological toxicity
- >50% decrease in platelets or neutrophils from Cycle 0 Day 1
- >2 g/dL decrease in hemoglobin from Cycle 0 Day 1
- Any ≥ Grade 2 drug-related non-hematological toxicity lasting >5 days or requiring clinical intervention, except Grade 2 fatigue, nausea, vomiting, diarrhea, or constipation
- Any adverse event (AE) of any grade limiting tolerability as assessed by the SRC

At Dose Level S, the cohorts will be expanded to a minimum of 3 participants to further evaluate safety, PK, and pharmacological activity. Evidence of pharmacologic activity can include Grade ≥ 2 drug-related toxicity at any cycle, PK

data demonstrating exposure levels predicted to be efficacious based on nonclinical studies, or other evidence of treatment-related activity as agreed on by the SRC. Dose decisions will be based on assessments in 2 or more dose-limiting toxicity (DLT) evaluable participants completing the DLT evaluation period. Any escalation of RP-1664 after Dose Level S will be in increments up to 75% as agreed upon by the SRC and will enroll cohort sizes of $N \ge 3$.

RP-1664 Escalation Dose Level	Escalation Plan
	Daily (mg) or % of previous dose
	increment
1	10 mg
2	Up to 30 mg
3 to S	Up to 100% increases until Dose Level S
S	Expand cohort at same dose
S1 to MTD or tolerated and	Up to 75% increases until MTD or tolerated
pharmacologically active dose	and pharmacologically active dose

Evaluation of the PK data after at least 6 participants, with sufficient data to derive PK parameters, may trigger adjustment of the daily dosing frequency of RP-1664 to allow for twice-daily (BID) dosing. BID dosing may be initiated based on observed participant outcomes and PK parameters such as, but not limited to, t1/2 is < 12 hours or the C_{max} : C_{min} ratio is > 10. Any decision to move from QD to BID dosing during the trial will be made after consultation with the SRC. If BID dosing is initiated, the Sponsor in agreement with SRC, can elect to continue or cease enrollment in QD dosing cohorts based on available data.

Additional treatment schedules, including daily dosing, 3 days on/4 days off, 1 week on/1 week off, or 2 weeks on/2 weeks off may also be explored to mitigate AEs and/or improve efficacy. If an additional schedule is tested, the starting dose of RP-1664 may be as high as the highest total daily dose that cleared DLT evaluation. The decision to test one or more of these schedules and set the starting dose level will be agreed upon by the SRC and will take into consideration all available safety, efficacy, pharmacodynamic, and PK data.

The food effect portion of the trial will be conducted at selected centers and may start at Dose Level 3 or once Dose Level S is reached. The fasting recommendation for RP-1664 in the general trial population may be revised to allow dosing with food after at least 4 participants have been evaluated in the food effect portion of the trial.

Expansion cohorts may be opened if at least one safe dose and schedule at which clinical activity is identified and agreed upon by the SRC. Up to 20 efficacy evaluable participants in each expansion cohort can be enrolled to further evaluate the safety, PK, pharmacodynamic, and preliminary efficacy of RP-1664 at the selected dose level(s). Enrollment in expansion cohorts may be limited to specific tumor types and/or genomic profiles based on assessment of clinical activity by the Sponsor in the dose escalation portion and other emerging preclinical, translational, and clinical data external to the trial.

4.2 Study Procedure and Assessment

The trial will consist of a Pre-Screening Period (within 6 months from time of the Screening/Main Informed Consent Form [ICF] signature, to confirm molecular eligibility), Screening Period, Treatment Period (including PK evaluation period starting at cycle 0 Day 1, and continuing in 21- or 28- Day cycles), an End of Treatment (EOT) Visit (occurring within 7 days after the last dose of trial treatment), a Safety Follow-up Visit (occurring within 30 days \pm 14 days after the last dose of trial treatment), and a Survival Follow-up Period (survival follow-up assessments will be done every 90 days [\pm 14 days] after the date of treatment discontinuation until the end of trial [for up to 6 months after EOT] unless the participant

withdraws consent to the trial, the trial is terminated, the participant dies or is lost to follow-up), The end of Trial is defined as the date of the last visit (including all follow-up visit) of the last participant in the trial.

4.3 Sample Size

The approximate total number of participants exposed to RP-1664 will be 80. This will include approximately 40 DLT evaluable participants in dose escalation and 40 efficacy evaluable participants to be included in cohort expansion.

The sample size for dose escalation is not driven by statistics but determined based on number of dose escalations that will potentially be assessed. The sample size for the food effect and PK bridging portions of the trial were considered adequate to enable a preliminary assessment of potential food and formulation effect.

After one or more tolerated and clinically active doses/schedules are identified, based on discussion between the investigators and the sponsor, up to 2 expansion cohorts will be added to enroll selected tumor types or genotypes to further confirm the dose levels or establish a range for acceptable doses and assess efficacy required for a proof of concept. Up to approximately 20 efficacy evaluable participants will be enrolled in each expansion cohort (up to approximately 40 total evaluable participants). With the targeted response rate (Objective Response Rate [ORR]) of \geq 30%, this sample size (n=20) will provide approximately 80% power to reject the null hypothesis of ORR \leq 10%, with 1-sided type I error of 0.05. Specifically, at least 5 responses (out of 20 evaluable participants) are required for rejecting the null hypothesis.

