7. DEFINITIONS AND CONVENTIONS FOR DATA HANDLING

All analyses will be performed using SAS® Version 9.4 or higher.

Unless specified otherwise, the analyses of data collected will be descriptive and summaries will be presented separately for each dose level, dose schedule and in total for the specified analysis population. Statistical analysis will be purely descriptive and no formal hypothesis testing or comparative analysis between dose level and dose schedule will be performed. Confidence intervals (CIs) will be constructed at two-side 95% level where appropriate.

Frequency distributions for categorical variables will be provided as the number of subjects in the category and the percentages of the total number of subjects in the given population as noted. Percentages will be reported to one decimal place.

The descriptive statistics for continuous variables will be the number of subjects, mean, standard deviation, median, lower and upper quartile, minimum and maximum. Mean and median will be reported to 1 decimal place, while the standard deviation will be reported to 2 decimal places. Minimum and maximum will be reported the same as the original data.

Summary tables may be replaced with listings when appropriate. For instance, an AE Frequency table may be replaced with a listing if it only contains a few unique preferred terms (PTs) reported on relatively few subjects.

Shift tables will be utilized to summarize clinical laboratory tests and neurological exams when applicable.

All tables will be summarized by study cohorts, treatment, dose level and dose schedule and include an overall column unless otherwise specified.

All listings will be sorted by study cohorts, dose level and dose schedule, subject ID and, if applicable, by visit date unless otherwise specified in the text.

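### SAP 4.3 claims about 80% power for an expansion cohort of 20, but the stated rule of at least 5 responses has exact power of 76.2%, and no cut-off at n=20 reaches 80% within one-sided 0.05

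*SAP*

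**What the plan says.** SAP section 4.3 (Sample Size) sets the size of the expansion cohorts: "Up to approximately 20 efficacy evaluable participants will be enrolled in each expansion cohort", with up to two such cohorts. The null hypothesis is an ORR of 10% or less and the target is an ORR of 30% or more. The section states that "this sample size (n=20) will provide approximately 80% power to reject the null hypothesis" and that the test is run "with 1-sided type I error of 0.05". It then gives the decision rule: "at least 5 responses (out of 20 evaluable participants) are required for rejecting the null hypothesis". It does not say whether the power comes from an exact or an approximate calculation.

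SAP section 7 says of the analysis in general: "Statistical analysis will be purely descriptive and no formal hypothesis testing or comparative analysis between dose level and dose schedule will be performed". In the supplied documents, the power statement appears only in the SAP; the protocol synopsis does not repeat it.

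**The concern.** Section 4.3 gives every quantity needed to check its own power: the sample size, both response rates, the one-sided level and the rejection count. Responses are whole numbers, so at n=20 only a few combinations of type I error and power are attainable. The stated power does not belong to the stated rule.

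The sentence matters because it is the only quantitative justification visible for 20 participants per expansion cohort; the same section says that the dose-escalation size is not statistically driven. A reader of a cohort with 4 responses or fewer would take from the text that a drug with a 30% response rate gives such a result about 20% of the time. Under the stated rule it does so nearly 24% of the time.

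**Working it through.** **Inputs, all from SAP 4.3:** n = 20; p0 = 0.10; p1 = 0.30; one-sided alpha = 0.05; reject if X ≥ 5, where X is the number of responders.

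**Step 1. Where 80% can come from.** The uncorrected one-sided normal approximation is the likely source:

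- Required n = [(1.645·√(0.10·0.90) + 0.8416·√(0.30·0.70)) / 0.20]² = 19.3, rounded up to 20.
- Critical count at n = 20: 20·0.10 + 1.645·√(20·0.10·0.90) = 4.207.
- Power = P(Z > (4.207 − 6)/√4.2) = 0.809.

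This is close to the stated 80%. But a count above 4.207 means X ≥ 5, which is the SAP's own rule. The approximation and the SAP use the same test, and the approximation overstates its power.

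**Step 2. Exact power of the stated rule.** With X ~ Binomial(20, p), P(X ≥ 5) = 1 − Σ C(20,k) pᵏ (1−p)²⁰⁻ᵏ, summed over k = 0 to 4.

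- At p = 0.30: 1 − (0.0008 + 0.0068 + 0.0278 + 0.0716 + 0.1304) = 1 − 0.2375 = **0.7625**.
- At p = 0.10: P(X ≥ 5) = **0.0432**.

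**Step 3. Other cut-offs at n = 20 (exact).**

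| Reject if | Type I error at 10% | Power at 30% |
|---|---|---|
| X ≥ 4 | 0.1330 | 0.8929 |
| X ≥ 5 | 0.0432 | 0.7625 |
| X ≥ 6 | 0.0113 | 0.5836 |

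X ≥ 5 is the lowest cut-off within 0.05, so 76.2% is the highest power that any fixed cut-off attains. As an upper bound only, a randomised test spending the whole 0.05 would reject at exactly 4 responses with probability (0.05 − 0.04317)/0.08978 = 0.076. Its power would be 0.7625 + 0.076·0.1304 = 0.772, still short of 80%.

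**Step 4. Cross-check.** The continuity-corrected normal approximation to P(X ≥ 5) at p = 0.30 is P(Z > (4.5 − 6)/√4.2) = 0.768, in line with the exact value.

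**Step 5. Size of the gap.** 80% − 76.2% = 3.8 points. The type II error is 23.8% against an implied 20%. Under the same rule, exact power is 79.1% at a true ORR of 31% and 80.4% at 31.5%; it reaches 80% at about 31.3%.

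**The case against.** The text is hedged. It speaks of approximate power, an approximate cohort size and a target of 30% or more, and exact power does reach 80% at an ORR of 31.3%, inside that target range. The figure also has a respectable source in the usual normal-approximation formula. And little depends on it: the primary endpoint listed in SAP 5.2 is treatment-emergent adverse events, section 7 calls the analysis descriptive, and section 13 disclaims formal inference for the interim evaluations. The SAP's efficacy section and the full protocol are not visible and may name a method.

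Much of this stands as a limit on the consequence. It does not make the number right:

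- Power is conventionally quoted at the boundary of the alternative, here 30%, and 76.2% would more naturally be rounded to about 75% or 76%.
- The looseness in cohort size gives no help on the low side: with 19 participants and the same cut-off of 5, exact power is 71.8%.
- A method statement elsewhere could explain how 80% was obtained, but it could not change the probability of seeing 5 or more responses in 20.
- The descriptive label sits beside a section that still states a null hypothesis, an error level, a power and a rejection count.

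**Conclusion.** The concern holds, as a minor arithmetic error. The stated rule has exact power of 76.2% at an ORR of 30%, which is 3.8 points below the stated figure, and no cut-off at n = 20 gives 80% within one-sided 0.05. The cut-off of 5 in 20 is correct and the type I error is controlled at 0.043; only the power is overstated.

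The calculation assumes independent responses with a common response rate, exactly 20 evaluable participants in a cohort, and power evaluated at 30%. That the 80% came from an uncorrected normal approximation is an inference, since the SAP names no method; the conclusion does not depend on it.

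**What to change.** In SAP 4.3, replace the power figure with: approximately 76% power (exact binomial; actual one-sided type I error 0.043). Naming the normal approximation as the source would also serve, provided the exact 76% is given beside it. Leave n = 20, the one-sided 0.05 level and the cut-off of 5 unchanged.

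The SAP records its basis: "This document has been prepared based on Protocol Version 3.0". Only the protocol synopsis is available here, so the protocol needs a matching edit only if its full text carries the same sentence.

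The cost is one phrase, with no added participants and no change to any decision threshold. For scale only, the smallest single-stage design with exact type I error within 0.05 and at least 80% power is 25 participants with a cut-off of 6 responses (type I error 0.033, power 80.7%). The correction does not call for that.

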5. STUDY OBJECTIVES AND ENDPOINTS

5.1 Objectives

5.1.1 Primary Objectives

- To assess the safety and tolerability of RP-1664 in participants with eligible, advanced solid tumors
- To define a dose and schedule of RP-1664 that is tolerated and has clinical activity.

5.2 Primary Endpoints

• Incidence and severity of treatment-emergent adverse events (TEAEs)

6. ANALYSIS POPULATIONS

The following analysis populations will be used for statistical analysis.

6.1 DLT Evaluable Population

The DLT Evaluable Population will consist of participants who have met the minimum safety evaluation requirements of the trial and /or who experience a DLT at any time during the DLT evaluation period (from the start of treatment through the end of Cycle 1). Minimum safety requirements will be met if, during Cycle 1 of treatment, the participant receives at least 75% of their planned total dose of RP-1664, completes required safety evaluations, and is observed through the end of Cycle 1. This analysis set will be used for DLT analyses, unless otherwise specified.

6.2 Safety Population

The Safety Population, used for the assessment of overall safety and tolerability, will consist of all participants who receive at least 1 dose of RP-1664. The analysis set will be used for individual listings, disposition summary table and all safety analyses, unless otherwise specified.

7. DEFINITIONS AND CONVENTIONS FOR DATA HANDLING

All analyses will be performed using SAS® Version 9.4 or higher.

Unless specified otherwise, the analyses of data collected will be descriptive and summaries will be presented separately for each dose level, dose schedule and in total for the specified analysis population. Statistical analysis will be purely descriptive and no formal hypothesis testing or comparative analysis between dose level and dose schedule will be performed. Confidence intervals (CIs) will be constructed at two-side 95% level where appropriate.

Frequency distributions for categorical variables will be provided as the number of subjects in the category and the percentages of the total number of subjects in the given population as noted. Percentages will be reported to one decimal place.

The descriptive statistics for continuous variables will be the number of subjects, mean, standard deviation, median, lower and upper quartile, minimum and maximum. Mean and median will be reported to 1 decimal place, while the standard deviation will be reported to 2 decimal places. Minimum and maximum will be reported the same as the original data.

Summary tables may be replaced with listings when appropriate. For instance, an AE Frequency table may be replaced with a listing if it only contains a few unique preferred terms (PTs) reported on relatively few subjects.

Shift tables will be utilized to summarize clinical laboratory tests and neurological exams when applicable.

All tables will be summarized by study cohorts, treatment, dose level and dose schedule and include an overall column unless otherwise specified.

All listings will be sorted by study cohorts, dose level and dose schedule, subject ID and, if applicable, by visit date unless otherwise specified in the text.

7.1 Definition of Baseline

For all evaluations unless otherwise noted, baseline is defined as the most recent non-missing measurement within 28 days prior to the first administration of RP-1664.

- Change from baseline is calculated as (Value at a visit Baseline value).
- Percent change from baseline is calculated as (Value at a visit Baseline value)/Baseline value * 100.

7.2 Definition of Study Days

Unless otherwise noted, study days of an evaluation are defined as the number of days relative to the first dose date which is designated as Day 1, and the preceding day is Day -1, the day before that is Day -2, etc.

Study days are calculated as

- (Date of assessment first dose date + 1) for assessments on/after first dose date.
- (Date of assessment first dose date) for assessments before first dose date.

7.3 Analysis Visit Window

Data will be analyzed by scheduled visits, where appropriate. Data that are collected from an unscheduled visit will not be included in the by-visit summary tables but will be presented in the listings. However, data collected at unscheduled visits will also be considered for toxicity grading for laboratory assessments. Both unscheduled and out-of-window imaging assessments will be included in efficacy analysis.

7.4 Handling of Partial Dates for Adverse Events

If the year of the start date is missing or the start date is completely missing, the first dose date will be used. If the year of the end date is missing or the end date is completely missing, the event will be regarded as ongoing and do not impute. Impute AE end date first if both AE start date and end date are partially missing.

If end date of an adverse event is partially missing, impute as follows:

- If the day of the month is missing, the onset day will be set to the last day of the month.
- If the onset day and month are both missing, the day and month will be assumed to be December 31.
- If the imputed end date > death date, then set to death date.

If start date of an adverse event is partially missing, impute as follows:

- If the day of the month is missing, the onset day will be set to the first day of the month unless it is on or after the same month and year as study treatment. In this case, the onset date will be assumed to be the first dose date of treatment.
- If the onset day and month are both missing, the day and month will be assumed to be January 1 when the year is on or after the year of study treatment. If the year is prior to year of first dose, December 31st will be used. The event onset will be coded to the first dose date of treatment if year is the same as the year of first dose date to conservatively report the event as treatment-emergent.
- If the imputed AE start date is after the AE end date (maybe imputed), then update the AE start date with the AE end date as the final imputed AE start date.
- If the imputed start date > death date, then set to death date
- If the imputed end date is before imputed start date, the AE event will be treated as treatment emergent AE and report it as data issue.

Imputation of partial dates is used only to determine whether an event is treatment-emergent; data listings will present the partial date as recorded in the eCRF.

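### SAP 7.4 back-dates AE onsets with a missing day in any later month to the first dose date, and two of its bullets can give one event opposite treatment-emergent status

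*SAP*

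**What the plan says.** All the rules at issue are in SAP 7.4.

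- **Onset with the day missing:** the default is the first of the recorded month, with an exception: "unless it is on or after the same month and year as study treatment. In this case, the onset date will be assumed". The value assumed under the exception is the first dose date.
- **Onset with day and month missing:** "the day and month will be assumed to be January 1 when the year is on or after the year of study treatment". An earlier year takes 31 December. A later sentence adds: "The event onset will be coded to the first dose date of treatment if year is the same as the year of first dose date".
- **Imputed start after the end date (third start-date bullet):** "then update the AE start date with the AE end date as the final imputed AE start date". This bullet notes that the end date may itself be imputed.
- **Imputed end before imputed start (last start-date bullet):** "If the imputed end date is before imputed start date, the AE event will be treated as treatment emergent AE", and the record is also logged as a data issue.

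Partial end dates go to the last day of the month, or to 31 December if the month is missing too. The section closes by confining imputation to the decision on TEAE status. SAP 12.2 ends the TEAE window 30 days after treatment stops or at the start of other anticancer therapy, whichever comes first. Treatment-related SAEs count as TEAEs whatever their onset. SAP 5.2 makes the incidence and severity of TEAEs the primary endpoint.

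**The concern.** The first rule discards information. If the month of onset is known and is later than the first-dose month, the event began after dosing and there is nothing to resolve in favour of Day 1. The only month that needs the exception is the first-dose month itself, where the onset could fall on either side of the first dose.

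The third and last bullets describe the same situation (start later than end) and do different things with it. One produces a date that can precede dosing; the other assigns treatment-emergent status outright. With no order of precedence, two programmers following the text could produce different TEAE counts for the primary endpoint. That endpoint is tabulated by dose level and schedule, where cohorts are small.

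**Working it through.** The plan gives no figure to reproduce. The rules were applied literally to worked dates. Assumed dates: first dose 15 March 2025, last dose 20 May 2025, no new anticancer therapy. The TEAE window then closes on 20 May + 30 days = 19 June 2025. SAP 7.2 defines study days as "the number of days relative to the first dose date which is designated as Day 1", so study day = date − first dose date + 1.

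**Step 1: the back-dating rule.** The last two columns confine the exception to the first-dose month and use the first of the month afterwards.

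| Onset recorded | SAP 7.4 as written | TEAE | First of month for later months | TEAE |
|---|---|---|---|---|
| March 2025 | 15 March 2025, Day 1 | yes | 15 March 2025, Day 1 | yes |
| April 2025 | 15 March 2025, Day 1 | yes | 1 April 2025, Day 18 | yes |
| June 2025 | 15 March 2025, Day 1 | yes | 1 June 2025, Day 79 | yes |
| July 2025 | 15 March 2025, Day 1 | **yes** | 1 July 2025, Day 109 | **no** |
| February 2026 | 15 March 2025, Day 1 | **yes** | 1 February 2026, Day 324 | **no** |
| 2026 only | 1 January 2026, Day 293 | no | 1 January 2026, Day 293 | no |

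The flag changes only for July 2025 and February 2026, the months lying wholly after 19 June. The last two rows show the inversion: the record that names a month goes back to Day 1, while the one that gives only the year stays in 2026.

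**Step 2: comparison with SAP 7.5.** The medication rule there separates three cases: a month after first dose takes the first of the month, a month before it takes the last day, and the same month takes the first dose date. SAP 7.4 merges the first and third.

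**Step 3: the two bullets.** Take an onset recorded as 2025 only and an end recorded as February 2025.

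- Imputed end: 28 February 2025.
- Imputed start: 15 March 2025, because the year is the first-dose year.
- Third bullet: the start becomes 28 February 2025, before first dose. Not a TEAE.
- Last bullet: the imputed end precedes the imputed start. TEAE.
- SAP 12.2: the event was over before exposure, so it can neither be new nor worsen after it. Not a TEAE.

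**Step 4: is the conflict reachable more generally?** The rules were run on a grid of 55,944 chronologically possible partial-date records (36 first-dose dates in 2025; onset and end years 2024 to 2026). Start fell after end in 1,272. In every one the end preceded first dose, so the third bullet gives a pre-dose start. The end date was imputed, as the last bullet's wording requires, in 594. These are 198 year-only onsets in the first-dose year and 396 year-only onsets in the year before (198 + 396 = 594); the latter arise because the start goes to 31 December. The counts show that the conflict can occur, not how often it will.

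**The case against.** The case for leaving the text alone is mainly about size, and most of it stands.

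- Inside the window, a later-month onset is a TEAE under either rule. SAP 12.2 also ends AE recording at the same point as the TEAE window, so few post-window onsets should reach the database. It requires missing onset dates to be queried as well.
- SAP 7.4 says it means to lean towards treatment-emergent status. That explains the rule for the first-dose month and year. It does not explain a rule whose only effect on the flag is to include events known to have begun after the window.
- The third bullet calls its result final. Applied first, it makes start equal to end, and the last bullet can no longer fire. That is a sensible reading, but the SAP states no order, and under it the TEAE assignment in the last bullet has no function.

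A reader might infer three stronger points that the documents do not support.

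- *That late events in general cannot be excluded.* Only onsets with a missing day are affected; complete dates are untouched.
- *That the conflict covers any event with a known end date before first dose*, such as onset March 2025 and end 10 March 2025. The last bullet speaks of an imputed end date, and that one is complete. On the wording, only the third bullet applies, and the event is correctly not a TEAE.
- *That DLT timing or event durations are distorted.* Imputed dates are used for TEAE status alone.

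**Conclusion.** Both rules are wrong as written, and the consequence is minor. The back-dating rule misclassifies only events with a missing onset day whose known month lies wholly after the TEAE window, other than treatment-related SAEs, which count regardless. The bullet conflict, on its exact wording, needs an onset with the month also missing and a partial end date before first dose. Adverse events are recorded from consent, so such records should be rare.

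The documents do not allow a frequency to be estimated; the worked dates are illustrative. The example in which the onset is recorded as 2025 only also assumes that the sentence setting same-year onsets to the first dose date overrides the 1 January clause before it, which appears to be the intention. This is worth correcting because it affects how the primary endpoint is counted and the correction is not contentious, but no conclusion of the trial is likely to depend on it.

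**What to change.** In SAP 7.4:

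1. Confine the missing-day exception to onsets in the same month and year as the first dose, and use the first of the month for later months, as SAP 7.5 does. An onset in the month in which the window closes stays a TEAE if the first of that month is inside the window, which keeps the conservative intent.
2. Keep the third start-date bullet.
3. Reduce the last bullet to logging a data issue, as the parallel bullet in SAP 7.5 does, and drop the TEAE assignment. Restricting that bullet to events without a complete end date would not help, because imputed end dates are where the literal conflict lies.
4. State that an event whose end date, complete or imputed to its latest possible date, is before first dose is not treatment-emergent.

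The same edit could make the 1 January clause apply only to years after the first-dose year, so that it no longer overlaps with the sentence on same-year onsets.

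The cost is SAP wording and a few lines of derivation code, best done before programming is finalised. Trial conduct and data collection do not change.
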